### *Analysis*

A mixed factorial ANOVA will be conducted to assess differences in SBR between conditions, in addition to an ANCOVA (to control for covariates related to SBR rates such as age, number of strips of tape, and levels of skin barrier impairment; Law et al., 2020; Robinson et al., 2017). For the secondary outcomes (biological, physiological, and psychological measures), mixed factorial ANOVAs will be conducted to analyse the main and interaction effects of time-point and condition. The data will be checked for violations of the normality assumption before analysis. To investigate whether psychological and physiological stress levels mediate the relationship between the delivery condition and SBR, separate exploratory mediational analyses will be conducted.

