## **Hypotheses**

1. It is hypothesised that both the digital human and audiotape conditions will have improved SBR after a tape-stripping wound, as assessed by trans-epidermal water loss (TEWL), compared to the control group, who did not receive a relaxation intervention (only magazines).
2. It is hypothesised that there will be no differences in SBR after a tape-stripping wound, as assessed by TEWL, between the digital human and audiotapes condition.
3. It is hypothesised that the relationship between relaxation and SBR will be mediated by levels of stress (biological, physiological, and self-reported) .
4. It is hypothesised that the digital human condition will have greater improvements in anxiety, stress, pain and relaxation levels and better compared to the audiotape delivery and magazines (control group).

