## **Method**

### ***Study design.***

This randomised controlled trial will use a 3 (time-point) x 3 (condition) mixed factorial experiment to investigate the effects of different delivery methods (digital human v audiotape v control) of relaxation on SBR after tape-stripping.

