Participants allocated to the digital intervention will complete the digital human delivered relaxation intervention for 25 mins. During this time, the digital human will guide participants through progressive muscle relaxation and guided deep breathing. Those in the audiotape condition will be instructed to follow instructions on the computer (using the same script as the digital human condition). Those allocated to the control condition will be told to wait 25 minutes for their skin to recover while given magazines to read. The researcher will leave the room but will be next door in case there are any issues.

The researcher will return to the room once the intervention period is over, and participants will be asked to complete the post tape stripping questionnaires and the final TEWL measurements and saliva sample. The TEWL measured after the intervention period will be used to calculate SBR, an index of how fast the skin barrier recovered from the skin barrier disruption caused by the tape-stripping procedure. At the end of the session, participants will be given a \$30 voucher as compensation for their time.

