### ***Baseline Measures***

These are measured to describe the sample and control for any differences between groups, because these variables have been previously shown to affect healing and immune parameters (Law et al., 2020a, 2020b; Robinson et al., 2015).

**Demographics.** Participants will be given a demographics questionnaire which includes questions regarding age, weight, height, ethnicity, and education level. Collecting data on these variables will allow for subgroup analysis and comparisons of the groups at baseline.

**Health behaviours.** Participants will be given a questionnaire that includes questions about alcohol consumption, physical exercise, diet, smoking status, and sleep. Alcohol consumption will be assessed from 1 (never) to 6 (every day) in the past three months. Participants will be asked how often they did physical exercise for more than 30 minutes in an average week from 1 (never) to 8 (every day). Diet will be assessed from 1 (very poor) to 5 (very good) in the past week. Participants will be asked to give their smoking status and the number of hours slept in the past 24 hours.

**Perceived stress.** The Perceived Stress Scale (PSS) measures the appraisal of how stressful situations in one's life are perceived (Cohen, 1983), and will be assessed at baseline only. It uses a 10-item Likert scale to rate how often respondents felt or thought a certain way in the last month from 0 (never) to 4 (very often). Scores are totalled across items and range between 0 and 40. High scores on the PSS indicate participants are experiencing a greater level of perceived stress. The scale has shown good reliability ( $\alpha > .70$ ) and validity in different ethnicities and clinical samples (Lee, 2012).

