### *Primary outcome measures*

**Tape stripping and SBR.** The final SBR value for each site is determined by the TEWL readings from the three time-points. An overall TEWL reading comes from averaging 20 consecutive measurements with a standard deviation below 0.5 for each site and time point. To get the SBR percentage from the TEWL readings the following formula is used:  $(TEWL_{elevated} - TEWL_{recovery}) / (TEWL_{elevated} - TEWL_{baseline}) \times 100$  (Robles, 2007; Robles et al., 2009). A higher percentage means a higher SBR during the intervention period (faster wound healing). SBR values will be excluded if there is incomplete data, are more than two standard deviations above the mean, or sites are not within 30g/m^2h of each other (Law et al., 2020a). This outcome has concurrent validity with gravimetrically assessed absolute water loss rates (Fluhr et al., 2006).

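### The primary analysis and sample size give SBR a time-point factor that it lacks, and neither the deciding analysis nor a test that both relaxation arms beat control is fixed

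*Protocol*

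**What the plan says.** - **Protocol, Study design:** the effect of delivery method on SBR is studied in a "3 (time-point) x 3 (condition) mixed factorial experiment".
- **Protocol, Analysis:** "A mixed factorial ANOVA will be conducted to assess differences in SBR between conditions, in addition to an ANCOVA". The ANCOVA adjusts for "covariates related to SBR rates such as age, number of strips of tape, and levels of skin barrier impairment". Neither analysis is named as the deciding one, and no comparison between particular arms is stated.
- **Protocol, Primary outcome measures:** "The final SBR value for each site is determined by the TEWL readings from the three time-points". The formula divides the fall in TEWL (trans-epidermal water loss) from the elevated to the recovery reading by the rise from baseline to elevated, times 100.
- **Protocol, Procedure:** "The TEWL measured after the intervention period will be used to calculate SBR". SBR is therefore obtained once, at the end of the session.
- **Protocol, Hypotheses:** hypothesis 1 is that "both the digital human and audiotape conditions will have improved SBR after a tape-stripping wound" compared with the magazine control.
- **Protocol, Participants (sample size):** a G*Power calculation for a mixed factorial ANOVA with f = 0.30, two-tailed alpha 0.05 and power 0.80 gives 75, raised by 20% to 90 (30 per arm).

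**The concern.** The three time-points are used up in forming SBR. What remains is one value per test site, or one per participant once sites are averaged, and nothing varies over time. The factor named in the design does not exist for the outcome it is meant to analyse.

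Two further problems follow from the same text. First, an ANOVA and an ANCOVA of the primary outcome stand side by side without an order, so the trial could end with two primary p-values that disagree. Second, hypothesis 1 makes two claims, one for each relaxation arm against control, whereas a three-arm omnibus F only says that the arm means are not all equal.

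The sample size was calculated for the same mixed model. If it takes credit for repeated measures that SBR does not supply, the stated 80% power does not apply to the primary outcome.

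**Working it through.** **Inputs from the protocol:** three conditions, three time-points, f = 0.30, alpha 0.05 two-tailed, power 0.80, N = 75 raised to 90, equal allocation. **Not in the protocol, so assumed:** the correlation between repeated measures, the split of the effect between the two relaxation arms, and the variance explained by covariates.

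**1. Reproducing 75.** For the between-groups test of a repeated-measures ANOVA with k = 3 groups, m measures and correlation rho, the noncentrality is λ = f²·N·m / (1 + (m − 1)·rho), with df = (k − 1, N − k).
- With m = 3, rho = 0.5, N = 75: λ = 0.09 × 75 × 3 / 2 = 10.125, power 0.803. N = 72 gives 0.785. The stated 75 is reproduced.
- The same test with rho = 0, 0.25, 0.75, 0.9 needs 39, 57, 93, 105.
- With m = 3 and rho = 0.5, the interaction test needs 27 and the within-participant test 21.
- The inflation is 75 × 1.2 = 90.

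**2. One SBR value per participant (m = 1).** Now λ = f²·N.
- N = 75: λ = 6.75, omnibus power 0.62.
- N = 90: λ = 8.10, omnibus power 0.71.
- Power 0.80 needs N = 111.

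**3. What the omnibus F can show.** At f = 0.30 and N = 90 its power is 0.71 when both relaxation arms beat control. It is also 0.71 when only the audiotape arm differs, and when one relaxation arm is worse than control. A significant F does not tell these patterns apart, and only the first agrees with hypothesis 1.

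**4. Power of the comparisons that do address hypothesis 1.** Suppose both relaxation arms exceed control by the same d. For arm means (0, d, d), f = d·√2/3, so d = 0.30 × 3/√2 = 0.636. With n per arm and pooled error (df = 3n − 3), the noncentral t parameter is d/√(2/n) for one arm against control and d/√(1.5/n) for both arms pooled against control.

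| Test at 0.05, unadjusted | 90 analysable (n = 30) | 75 analysable (n = 25) |
|---|---|---|
| Pooled relaxation vs control | parameter 2.85, power 0.80 | parameter 2.60, power 0.73 |
| Each arm vs control | parameter 2.46, power 0.68 | parameter 2.25, power 0.60 |
| Both arms vs control (400,000 simulated trials) | 0.54 | 0.44 |

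The 75 column applies if all 15 extra participants are lost to measurement errors. Power of 0.80 for each arm against control needs 40 per arm (120).

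**5. Gain from covariates.** If they explain a share R² of the SBR variance, the error SD shrinks by √(1 − R²). With R² assumed at 0.1, 0.2 and 0.3 and N = 90, the pooled contrast has power 0.84, 0.88 and 0.92, and each arm against control has 0.73, 0.78 and 0.83.

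**The case against.** **The SBR analysis might be read as unrunnable.** The documents do not support that. The Analysis section's sentence on SBR does not itself mention time-point. SBR is defined per site and there are three stripped sites, so a site-by-condition mixed ANOVA would run. The ANCOVA in the same sentence runs on one value per participant. This stands against the stronger reading, but it does not reconcile the text: Study design names time-point, and no section names site as a factor. If sites were meant, 75 would still rest on an unstated between-site correlation of 0.5. At 0.75 to 0.9 the same calculation needs 93 to 105.

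**A reader might infer that any workable version dilutes the effect,** because a condition main effect on raw TEWL averages two readings taken before allocation with one taken after. But an effect present only after the intervention is carried by the time-by-condition interaction. Simulated with 0.64 SD at the last time-point and 30 per arm, the interaction has power of about 0.58, 0.74 and 0.94 at correlations 0.3, 0.5 and 0.7. That also assumes that f = 0.30, given for SBR, carries over to raw TEWL. General dilution is not shown. The interaction is nevertheless a 4-df test on a different outcome and does not show that each arm beats control.

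**The Baseline Measures section might be read as choosing covariates by observed imbalance,** since it speaks of measuring variables to "control for any differences between groups". The same sentence justifies those variables by their known relation to healing. It states no rule of selecting by imbalance.

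**Contrasts, multiplicity and the final covariate list can be left to a SAP,** which is not at hand. That is fair, and their absence alone would be no finding. The ill-fitting factor, the two unranked analyses and the sample size are stated in the protocol itself.

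**Conclusion.** The point holds in this form. The mixed factorial design names a time-point factor that SBR does not have. Two analyses of SBR are given without an order. An omnibus test, whichever version is run, does not establish hypothesis 1.

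The stated 80% power does not apply to a single SBR value per participant. At the protocol's own f = 0.30 the one-way omnibus test has 0.62 at 75 and 0.71 at 90. This does not depend on a correlation or on how the effect is split between arms. Attributing 75 to three repeated measures with correlation 0.5 is an inference: it reproduces the figure exactly, but the protocol does not state the correlation. The contrast figures assume equal effects in both relaxation arms, and the adjusted figures assume that covariates explain 10 to 30% of variance.

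The primary outcome can still be analysed, and no loss of valid data is implied. What needs correcting is the model, the ranking of the analyses and the power statement.

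**What to change.** 1. Remove the time-point factor for SBR in Study design and Analysis. Keep it for the secondary outcomes measured at three time-points.
2. Name one primary analysis: ANCOVA of participant-level SBR (mean of valid test sites) on condition, with age, number of tape strips and post-stripping barrier impairment as fixed covariates. All three are known before the allocation envelope is opened.
3. Test hypothesis 1 by each relaxation arm against control. A pooled relaxation-versus-control contrast may come first as a gatekeeper, but it can succeed when only one arm works and does not itself establish the claim for both. With that gate at 0.05, each arm can then be tested at 0.05 (a closed procedure for two hypotheses). The gate costs no power for winning both: if both arms exceed control significantly, so does their pool, because its standard error is smaller.
4. Make the unadjusted one-way ANOVA a sensitivity analysis.
5. Restate the power in the sample size paragraph for the chosen test, at both 90 and 75 analysable, with the assumed effect pattern and any covariate gain written out.

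The cost is wording in the protocol and SAP, and no new data. The downside is a less favourable power statement: the sponsor must accept about 0.54 for both arms at 90 before covariate gain, or enlarge the trial. These comparisons with control do not address hypothesis 2, which claims no difference between the relaxation arms without a margin.

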After collecting baseline measures, the researcher will conduct the tape stripping procedure. Tape-stripping is a non-invasive experimental wound technique and standardised wound healing model that removes the outer layer of skin (the stratum corneum) through repeated application of the adhesive tape (Altemus et al., 2001; Irwin & Vedhara, 2007). By doing this, the skin cannot regulate water movement in and out of the skin, creating skin barrier disruption (Walburn et al., 2009). To get a baseline measure of this skin barrier function, a TEWL measurement will be obtained using a Tewameter 300 probe which measures the evaporation rate (g/m^2h) in the air layer next to the skin (Law et al., 2020b). TEWL, the skin's ability to prevent water loss, increases when the stratum corneum is disrupted and decreases when it heals. The probe must first be calibrated and preheated to 34°C (skin temperature), with constant ambient room conditions (Koschwanez & Broadbent, 2011). On each participant's non-dominant forearm, four 1cm^2 sites will be marked, with one

being the (undamaged) control. The probe will take one measurement every second for 60 seconds to measure the baseline values for each of the four sites one at a time. New pieces of tape will then be applied with pressure to the three test sites and gently peeled until the TEWL reaches 15 g/m^2h above baseline or 40 pieces of tape have been used. A TEWL measurement for each site will then be measured to examine the level of skin barrier impairment because of the tape-stripping. Immediately after the tape-stripping, participants will complete the post-tape-stripping questionnaire, the second saliva and TEWL measurements.

After the tape-stripping procedure, participants will be randomised to either the digital, audiotape, or control condition using a random online number generator by a researcher not involved in the study, completed in advance. Group allocation will be revealed after the researcher opens the sealed, opaque envelope containing each participant's assigned condition, after which the researcher will no longer be blinded to the conditions. As previous research has found that a relaxation session before and after tape-stripping can improve wound healing, this study will deliver the relaxation after the tape-stripping procedure for clinical practicality as there is often little time for relaxation to be done before an acute wound or pre-surgery (Robinson et al., 2015).

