### *Secondary outcome measures*

**Biological Measures.** Salivary cortisol and alpha-amylase are reliable and valid measures of stress-related biological markers of stress if standardised procedures (as above) to reduce confounders are used (Strahler et al., 2017). The collection of these samples is necessary to investigate whether the intervention had any effect on physiological stress and test the secondary hypothesis regarding stress mediating the relationship between relaxation and wound healing. Having these measures is important for further understanding of the underlying mechanisms through which relaxation works on stress and wound healing.

Saliva samples will be obtained at three-time points; baseline, after tape-stripping and after the intervention period, using standardised SaliCaps collection devices (IBL, Hamburg, Germany). Participants will be asked to rinse their mouth with water beforehand and not

swallow for two minutes to collect saliva in their mouth naturally, using the passive drool technique, before transferring their saliva into the SaliCap. After collection, the saliva samples will be stored at  $-20^{\circ}\text{C}$  at the University of Auckland and then shipped for analysis on dry ice to the University of Vienna. Cortisol concentrations will be determined using commercial enzyme-linked immunosorbent assay (ELISA, IBL, Hamburg, Germany), while alpha-amylase will be determined by a kinetic colorimetric test with reagents from Roche (Roche Diagnostics, Mannheim, Germany; Law et al., 2020a; Robinson et al., 2017).

**Physiological measures.** Participants will wear a wrist sensor (Empatica E4) which will continuously measure blood volume pulse and electrodermal activity for the duration of the session. Blood volume pulse will be converted into a measure of heart rate. Electrodermal activity will be used to measure changes in electrical resistance in the skin (skin conductance). Heart rate and skin conductance will be used as physiological measures of stress and relaxation.

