**Psychological measures.** Participants will be given a visual analogue scale at the three time points to measure participants level of relaxation, stress, anxiety, and pain where they are required to mark a cross on a 100mm line how they are currently feeling. Scores are derived by using a ruler and measuring the distance (in mm) from the "not at all" anchor to the cross the participant placed on the line. A high score indicates that at the current time the participant has greater intensities of felt stress, anxiety, and pain and lower levels of relaxation.

The relaxation scale ranges from "not relaxed at all" to "extremely relaxed", the stress scale from "not at all stressed" to "extremely stressed", the anxiety scale from "not at all anxious" to very anxious" and the pain scale from "no sensation of pain" to "most sensation

of pain imaginable". These measures have been used in previous tape stripping and psychological intervention studies to assess participant psychological state (Law et al., 2020a; 2020b; Robinson et al., 2015).

**Relaxation Delivery Feedback.** There will be two visual analogue scales (on a 100mm line) asking about participant's satisfaction and engagement during the relaxation session from "not engaging at all" to extremely engaging" and "not at all satisfied" to very satisfied". The second part of this section is qualitative and will ask participants to write what they liked about the session's delivery and how it can be improved. These questions have been adapted from Loveys and colleague's feasibility study investigating digital humans and CBSM (in prep). Including this questionnaire is necessary to understand how people respond to the digital human.

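### For saliva markers and state VAS items, the planned 3 x 3 ANOVA is a valid but inefficient treatment test, because two of its three time points precede allocation

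*Protocol*

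**What the plan says.** The Study design section describes a "3 (time-point) x 3 (condition) mixed factorial experiment". Under Analysis, the secondary outcomes (biological, physiological and psychological) are assigned one method: "mixed factorial ANOVAs will be conducted to analyse the main and interaction effects of time-point and condition". ANCOVA is named for the primary outcome, skin barrier recovery (SBR), only: "A mixed factorial ANOVA will be conducted to assess differences in SBR between conditions, in addition to an ANCOVA". Its listed example covariates are age, number of tape strips and level of barrier impairment. No secondary outcome is given an analysis adjusted for its own earlier values.

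The timing is set out elsewhere:

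- Saliva: "Saliva samples will be obtained at three-time points; baseline, after tape-stripping and after the intervention period".
- State scales for relaxation, stress, anxiety and pain: "Participants will be given a visual analogue scale at the three time points".
- The second of these measurements, under Procedure: "Immediately after the tape-stripping, participants will complete the post-tape-stripping questionnaire, the second saliva and TEWL measurements".
- Allocation, also under Procedure: "After the tape-stripping procedure, participants will be randomised to either the digital, audiotape, or control condition". The random list is prepared in advance, but the sealed envelope is opened only at this stage.
- The intervention: "this study will deliver the relaxation after the tape-stripping procedure for clinical practicality".

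Hypothesis 4 predicts greater improvement in anxiety, stress, pain and relaxation with the digital human than with either audiotape or magazines.

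**The concern.** Neither participant nor researcher knows the condition at the first two measurements, and no relaxation has been given. Any group difference there is chance. The treatment effect can appear only in the third value, so the comparison that randomisation supports is the difference in that value given the starting level.

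The 3 x 3 ANOVA spreads that single comparison over two tests. The condition main effect averages two null differences with one real one. The interaction has 2 x 2 = 4 degrees of freedom. Under compound symmetry the whole signal sits in the 2-df contrast of the third point with the mean of the first two. The other 2 df compare the groups on the change from baseline to post-stripping, which treatment cannot influence.

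These outcomes answer hypothesis 4, and they show whether the intervention changed stress at all, which the mediation aim depends on. A real effect is more likely to be missed than it need be with the data already planned.

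**Working it through.** **Inputs from the protocol (Sample size).** Two-sided alpha 0.05; power 0.80; f = 0.30, stated for SBR; required N = 75; final N = 90, 30 per group.

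**Assumptions not in the protocol.** The same f = 0.30 applies to a secondary outcome, at time 3 only. Variances are equal and the correlation r between any two time points is the same (compound symmetry), with r = 0.3, 0.5, 0.7 and 0.8. When one arm differs from two equal arms, f = 0.30 means a difference of 3 x 0.30/√2 = 0.64 SD.

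**Reproducing the plan's own figure.** Between-groups test in a repeated-measures ANOVA with m = 3 measurements: λ = f²·N·m/[1+(m−1)r], df 2 and N−3. With r = 0.5 (assumed) and N = 75, λ = 0.09 x 75 x 3/2 = 10.125 and power is 0.803. 75 x 1.2 = 90. So 75 fits a condition main effect that is present at all three points.

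**Effect at time 3 only, N = 90.**

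- Condition main effect: the averaged difference is (0 + 0 + d)/3 = d/3, so λ = (f/3)²·N·3/(1+2r), df 2, 87. At r = 0.5: 0.01 x 90 x 3/2 = 1.35.
- Interaction: λ = f²·N·(2/3)/(1−r), df 4, 174. At r = 0.5: 8.1 x 0.667/0.5 = 10.8.
- ANCOVA on both earlier values: λ = f²·N/[1−2r²/(1+r)], df 2, 85. At r = 0.5: 8.1/0.667 = 12.15.
- ANCOVA on the post-stripping value alone: λ = f²·N/(1−r²), df 2, 86. At r = 0.5: 8.1/0.75 = 10.8.
- One pairwise contrast of 0.64 SD from the two-covariate ANCOVA: λ = d²·15/[1−2r²/(1+r)], df 1, 85. At r = 0.5: 0.405 x 15/0.667 = 9.11.

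| Power at r = | 0.3 | 0.5 | 0.7 | 0.8 |
|---|---|---|---|---|
| Condition main effect | 19% | 16% | 14% | 13% |
| Interaction (4 df) | 57% | 74% | 94% | 99.2% |
| ANCOVA, both earlier values | 77% | 88% | 98% | 99.8% |
| ANCOVA, post-stripping value only | 75% | 83% | 95% | 99.1% |
| Pairwise contrast, two-covariate ANCOVA, unadjusted | 75% | 85% | 96% | 99.5% |

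Interaction against two-covariate ANCOVA: a loss of about 20, 14, 4 and 0.6 percentage points.

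Simulation (3,000 trials per correlation) agrees within about two points. For main effect, interaction and two-covariate ANCOVA it gave 0.187, 0.590 and 0.772 at r = 0.3; 0.156, 0.731 and 0.858 at r = 0.5; and 0.139, 0.935 and 0.973 at r = 0.7.

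At r = 0.5, 80% power needs N = 648 for the main effect, 102 for the interaction and 75 for the two-covariate ANCOVA.

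**The case against.** The strongest reply is that the protocol plans the interaction as well as the main effects. Hypothesis 4 speaks of greater improvement, meaning differential change over time, and the interaction tests that. This stands. A reader might infer from the main-effect row that the secondary outcomes have only about 16% power, or that no planned test addresses hypothesis 4. The documents support neither reading. The fair comparison is interaction against ANCOVA.

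The loss also depends on unstated inputs. All measurements fall within one session, so correlations of 0.8 or more cannot be excluded, and there the gap all but closes. Against ANCOVA on the post-stripping value alone, the loss is about 18, 9 and 1 points at 0.3, 0.5 and 0.7. This stands too and limits the size of the point.

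The gain shrinks once hypothesis 4 is split into two comparisons. With Bonferroni correction for two, the pairwise contrasts have about 65%, 77% and 93% power, close to the interaction at 0.5 and 0.7. But a significant interaction does not say which arm differs and would need follow-up contrasts of its own, so this narrows the advantage without reversing it.

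A reader might also infer that chance differences before allocation raise the false-positive rate. They do not: the interaction keeps its 5% level under sphericity or a correction for its violation, and such chance differences are part of that 5%.

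Finally, exact contrasts and intervals are commonly left to a SAP, so their absence is not the point here. The point is that the protocol names a test that fits its own timing poorly.

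**Conclusion.** The point holds as one of efficiency. For salivary cortisol, alpha-amylase and the four state VAS items, the condition main effect is diluted to exactly one third when the effect exists only after the intervention, and it should not be read as a treatment test. The planned interaction is valid but gives up about 20, 14 and 4 percentage points of power at correlations of 0.3, 0.5 and 0.7, and under 1 at 0.8, compared with an ANCOVA on data already being collected. These sizes rest on an assumed f = 0.30 at the third point, compound symmetry and 90 analysed participants.

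It is tempting to extend this to every secondary outcome, but the documents do not support that. Heart rate and skin conductance are recorded continuously with no stated mapping to three time points, and the satisfaction and engagement scales concern the session itself.

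**What to change.** In the Analysis section, make the between-condition test for cortisol, alpha-amylase and the four state VAS items an ANCOVA of the post-intervention value, with condition as factor and that outcome's baseline and post-stripping values as covariates. Take the two hypothesis 4 contrasts (digital human against audiotape, digital human against control) from this model, with 95% confidence intervals. Keep the three-time-point ANOVA for the time effect, which shows whether tape-stripping changed stress, and state that its condition main effect is not a test of treatment. Apply the same approach to heart rate and skin conductance only where pre-allocation summary values are defined.

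The cost is a change of wording. No extra participants, samples or visits are needed.

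### Two of the three readings in the secondary-outcome ANOVAs precede allocation, and the plan does not say which ANOVA effect tests the intervention; adjusting the final reading for the earlier two would be more powerful at no cost

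*Protocol*

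**What the plan says.** Under Study design, the trial "will use a 3 (time-point) x 3 (condition) mixed factorial experiment". Under Secondary outcome measures, "Saliva samples will be obtained at three-time points; baseline, after tape-stripping and after the intervention period", and for relaxation, stress, anxiety and pain, "Participants will be given a visual analogue scale at the three time points".

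The Procedure section fixes the order of events. The second set of readings comes first: "Immediately after the tape-stripping, participants will complete the post-tape-stripping questionnaire, the second saliva and TEWL measurements". Allocation follows: "After the tape-stripping procedure, participants will be randomised to either the digital, audiotape, or control condition". The random sequence is prepared beforehand by someone outside the study, but it stays concealed: "Group allocation will be revealed after the researcher opens the sealed, opaque envelope". The third set is collected after the 25-minute session: "The researcher will return to the room once the intervention period is over".

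For all secondary outcomes, the Analysis section then states that "mixed factorial ANOVAs will be conducted to analyse the main and interaction effects of time-point and condition". It does not single out one of these effects as the test of the intervention. The only ANCOVA it names is for skin barrier recovery (SBR), with age, number of tape strips and degree of barrier impairment as examples of covariates. The pre-allocation values of a secondary outcome are not used as covariates for that outcome.

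**The concern.** Participants and researcher learn the condition only after the second reading, so the expected difference between conditions is zero at readings 1 and 2. A model that treats all three readings as outcomes gives two effects involving condition, and neither is well aimed at the third reading. The main effect averages one informative reading with two uninformative ones. The interaction spreads its test over a comparison that cannot contain an effect.

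At stake are hypothesis 4 (anxiety, stress, pain and relaxation) and the question, raised under Biological Measures, whether the intervention changed cortisol and alpha-amylase. A real effect on these outcomes could be missed in a trial of 90 people although the data to detect it had been collected. If the main effect of condition were read as the effect of treatment, it would understate that effect.

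**Working it through.** **Inputs from the protocol.** Three conditions; three readings; 90 participants, 30 per group; two-tailed alpha 0.05; f = 0.30, stated for SBR only.

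**Assumptions not in the protocol.** The same f = 0.30 applies to a secondary outcome at the third reading, with no effect at readings 1 and 2. Variances are equal. Any two readings have the same correlation rho, taken as 0.5 with a range of 0.3 to 0.7.

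**The plan's own figure.** The required sample size of 75 can be reproduced as a between-condition main effect over three measurements at an assumed rho of 0.5. The noncentrality is f² × N × 3/(1 + 2 rho) = 0.09 × 75 × 3/2 = 10.125 on 2 and 72 df, which gives power 0.803; N = 72 gives 0.785. Raising 75 by 20% gives 90. That calculation is for SBR, and the protocol claims no power for the secondary outcomes.

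**Main effect of condition.** With expected differences of 0, 0 and delta at the three readings, the averaged difference is (0 + 0 + delta)/3 = delta/3. This is exact in raw units. Averaging also reduces the standard deviation, to sqrt((1 + 2 rho)/3) of its single-reading value, so the standardised effect falls to (1/3)/sqrt((1 + 2 rho)/3). That ratio is 0.46, 0.41 and 0.37 at rho 0.3, 0.5 and 0.7.

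**Interaction.** It has (3 − 1) × (3 − 1) = 4 df. Two belong to condition by (reading 1 versus reading 2), both before allocation and with expectation zero. Two belong to condition by (reading 3 versus the mean of readings 1 and 2), which carries the whole effect.

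**Noncentrality parameters, N = 90:**

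- Main effect: N f²/(3(1 + 2 rho)), on 2 and 87 df. At rho 0.5: 8.1/6 = 1.35.
- Interaction: (2/3) N f²/(1 − rho), on 4 and 174 df. At rho 0.5: 5.4/0.5 = 10.8.
- Contrast of reading 3 with the mean of readings 1 and 2, by condition: the same 10.8, on 2 and 87 df.
- ANCOVA of reading 3 on the earlier readings: N f²/(1 − 2 rho²/(1 + rho)). At rho 0.5: 8.1/(1 − 0.5/1.5) = 12.15. Under equal correlation the two earlier readings carry the same information as their mean. Error df are 86 with the mean as one covariate and 85 with two separate covariates, and power is the same to two decimals.

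**Power:**

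| Test | rho 0.3 | rho 0.5 | rho 0.7 |
|---|---|---|---|
| Main effect of condition, 2 df | 0.19 | 0.16 | 0.14 |
| Interaction, 4 df | 0.57 | 0.74 | 0.94 |
| Final versus earlier contrast, 2 df | 0.68 | 0.83 | 0.97 |
| ANCOVA, 2 df | 0.77 | 0.88 | 0.98 |

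A simulation of 20,000 trials at rho 0.5 gave 0.161 for the main effect and 0.736 for the interaction, in agreement with the formulas. To reach 80% power at rho 0.5, the main effect would need 648 participants, the interaction 102 and the ANCOVA 75.

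**The case against.** The strongest reply is that the plan already contains a sound test. In a design with readings before and after allocation, condition by time is a standard way to look for an effect, and it keeps its error rate: a separate simulation without any effect, at correlation 0.6, rejected in 0.050 of trials. This stands. A reader might infer that the planned analysis is invalid, and it is not. The loss is one of efficiency, and it shrinks as rho rises: from 0.88 − 0.74 = 0.14 against ANCOVA at rho 0.5 to 0.98 − 0.94 = 0.04 at rho 0.7. A 2-df contrast of the final with the earlier readings fits within the stated ANOVA and recovers much of the gap.

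Four other strong readings are tempting and also go too far.

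- *The plan takes the main effect of condition as its estimate of treatment.* The protocol lists main and interaction effects together and designates neither. The fair criticism is that the choice is left open when one candidate has almost no power.
- *Chance differences before allocation produce false positives in the main effect.* They cost precision, but the main effect rejected in 0.049 of the same simulated null trials.
- *Improvement in pain is meaningless because the first reading precedes the wound.* Hypothesis 4 does not define improvement as change from that reading, and the interaction also covers the change from after stripping to after the session.
- *Every secondary outcome is affected.* Heart rate and skin conductance are recorded continuously, and the protocol does not define time-points for them.

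It can also be said that contrasts and covariates are matters for a statistical analysis plan. That would answer a complaint about missing detail. Here the protocol does state a model for these outcomes, and that model makes poor use of the order of events that the protocol itself lays down.

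**Conclusion.** The point holds as one about efficiency and clarity for cortisol, alpha-amylase and the four VAS scales. Two results depend on no assumption about correlation: the main effect of condition estimates one third of the raw post-intervention difference, and half of the interaction's degrees of freedom compare pre-allocation readings. In standardised terms the reduction is to about 0.41 at rho 0.5, not to one third.

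The power figures are illustrative. They rest on an effect size stated only for SBR, on assumed correlations and on equal variances. Within that range the main effect is close to powerless whatever the correlation. The interaction is usable but always weaker than an ANCOVA on readings already collected. No stated figure is contradicted, because the protocol makes no power claim for these outcomes. The change is worth making because it costs nothing and removes the doubt over which result answers hypothesis 4.

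**What to change.** In the Analysis section, state that the effect of condition on cortisol, alpha-amylase and each of the four VAS scales will be tested by ANCOVA of the post-intervention value on condition, with the baseline and post-stripping values of the same measure as covariates. Report adjusted differences between conditions with 95% confidence intervals.

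Keep the time-point ANOVA as a description of the response to tape-stripping, and state that its main effect of condition will not be interpreted as a treatment effect. Apply the same model to heart rate and skin conductance only if they are summarised at the same three time-points.

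The cost is a change of wording: no new data, visits or participants. The only test given up compares conditions on readings taken before allocation.
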